## 4.2 Endpoints

#### 4.2.1 Primary outcome measure

The primary study endpoint is the occurrence of a re-rupture.

#### 4.2.2 Secondary outcome measures

Secondary endpoints are as follows:

- IKDC score
- Lysholm score
- Tegner Activity score

All of the above will be analysed only for patients with 5 years minimum follow-up post-procedure.

#### 4.2.3 Safety outcomes

Safety will be assessed by the recording of:

- Assessment of Adverse Events (AE)
- Assessment of Adverse Device Effects (ADE)

# 5 Study Methods

## 5.1 General Study Design and Plan

The study is a multicentre post-market clinical follow-up, with retrospective data collection. All patients were treated with the JewelACL for ACL between 1st October 2010 to 31st December 2014, and thus all have at least 5 years follow up post-surgery. The medical records of subjects will be evaluated, and all participants will receive a telephone call to collect patient reported outcomes.

## 5.2 Inclusion-Exclusion Criteria

#### 5.2.1 Inclusion Criteria

The participants must have met ALL of the following criteria to be considered eligible for the study:

- Age >18 years
- Previously implanted with the JewelACL for ACL reconstruction (Primary JewelACL cases only, no revision cases)

#### 5.2.2 Exclusion Criteria

Participants were not allowed to enter the study if ANY of the following applied:

- Age <18 years
- Any implantations for non-indicated conditions, as stated in the IFU
- Revision cases

# 5.3 Study Variables

## 5.3.1 Summary of study data and timing of measurements

The key study measurements, and the timing of these measurements are summarised in Table 1.

	Baseline	Procedure	Surgery to 6 months	6–24 months post	5 years post
Consent					х
Medical history	х				
Age / gender		х			
Surgical /		х			
procedure details		X			
Participation in	v		×	×	Y
sports	Х		Х	Х	х
Injury mode	х				
Re-rupture			х	х	х
Hybrid (with					
autograft) or non-		×			
hybrid (JewelACL		х			
only)					
Fixation type					
(tibial and		x			
femoral)					
Any other					
procedures		x			
recorded during					
ACL procedure					
Details of any					
complications or		х	x	х	х
revision of the		^		~	~
reconstruction					
IKDC Subjective	x			х	х
Knee Evaluation	X		х	Χ	^
Lysholm and	x		х	х	х
Tegner	^			^	^

Page 6 of 10

#### 5.3.2 Demographic and Baseline measurements

At the baseline timepoint, or time of the procedure, the following demographic and baseline characteristics of the study participants will be collected:

- Age
- Gender
- Medical History, including history of the knee(s) e.g. previous surgeries
- Participation in sports
- ACL failure injury mode
- Patient reported outcome scores

Additionally, information on the procedure will be collected:

- Hybrid (with autograft) or non-hybrid
- Fixation type (tibial and femoral)
- Other procedures during surgery (e.g. multi-ligament repair, meniscus repair)

# 6 Sample Size

The sample size was based on the primary outcome, occurrence of re-rupture. This was calculated to ensure an accurate estimate of this outcome. The failure rate was expected to be 10% (or less), based on data from Su et al. The sample size was calculated so that the uncertainty in the calculated value compared to the 'true' population percentage is not more than  $\pm 6\%$ . Using a 95% level of confidence, it was calculated that 96 subjects were required for the study. In order to allow for a 20% drop-out, 120 subjects were to be recruited into the study.

# 7 General Considerations

## 7.1 Timing of Analyses

A single analysis will take place at the completion of the study, after all data is collected. No interim analyses will be performed.

## 7.2 Analysis Populations

The Full Analysis Population will consist of all patients recruited into the study, as long as they had a minimum of 5-years of follow-up post-procedure.

Patients with missing data at a specific outcome timepoint will be excluded from this dataset only for the particular outcome for which they had missing data.

The safety population is the same as the full analysis population

## 7.3 Subgroups

In addition to an analysis of all patients combined, analyses for all outcomes (primary, secondary, safety) will be performed for the following subgroups:

- Patients receiving JewelACL alone
- Patients receiving JewelACL in combination with autograft

## 7.4 Missing Data

For the all analyses, only observed data will be analysed. Missing data will be assumed to be Missing At Random. No imputation procedures will be employed to deal with missing data.

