9.2 Informed Consent Process

The study design is retrospective data collection with a telephone call follow up at 5 years

post-surgery. Verbal consent will be required for all eligible patients who agree to consent to

the telephone follow-up, and this process is required to be recorded within the medical notes.

The Principal Investigator or his/her authorised designee will conduct the verbal informed

consent. This process will include a verbal discussion of all aspects of the study that are

relevant to the subject's decision to participate, such as the purpose of the study and

anticipated benefits. During the discussion, the Principal Investigator or his/her authorized

designee will avoid any improper influence on the subject and will respect the subject's legal

rights. If the subject agrees to give their verbal consent, then the Principal Investigator or

his/her authorised designee must document this process in the medical or research notes and

the process will be recorded within the Electronic Case Report Form.

Failure to obtain verbal informed consent from a subject to participate in the telephone follow

up will mean that the follow up telephone call must not take place. Retrospective data will

still be collected as no patient identifying data will be recorded.

Clinical Investigation Plan

CONFIDENTIAL

Page 18 of 42

The justification for verbal consent within this study is that it prevents the subject having to

return to the site to sign an informed consent form in person. This would put additional

burden on the patient, when the only data collected during the telephone follow up will be the

collection of patient outcomes using questionnaires e.g. IKDC Subjective Knee Evaluation,

Lysholm knee scoring scale and Tegner Activity and asking about any complications

experienced, all of which can be conducted over the phone.

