**Description of Statistical Methods** 

The primary analysis will summarise the re-rupture rate of patients. The number and percentage of

patients who have experienced a re-rupture will be reported. Additionally, a corresponding confidence

interval will be reported for the percentage of patients with a re-rupture. The analysis will be performed

for all patients combined, and also separately for the subgroups of patients receiving JewelACL alone,

and those receiving JewelACL in combination with autograft.

A single analysis will be performed at the end of the study, no interim analyses will be performed.

The Number of Participants

The sample size was calculated to ensure an accurate estimate of the re-rupture rate in patients

receiving JewelACL. Based on previous data and clinical experience, the re-rupture rate is expected to

be 10% (or less). The sample size was calculated so that the uncertainty in the calculated compared to

the 'true' population percentage is not more than  $\pm 6\%$ . Using a 95% level of confidence, it is calculated

that 96 subjects are required for the study. In order to allow for a 20% drop-out, 120 subjects will be

recruited into the study.

The Level of Statistical Significance

As there are no planned hypothesis tests, the level of significance is not relevant to this study. All

confidence intervals will be calculated using a 95% confidence level.

Criteria for the Termination of the Study

Not Applicable. The study will not be terminated based on any data collected.

Procedure for Accounting for Missing, Unused, and Spurious Data

The primary analysis will be performed on the collected data. No data imputations will take place, with

patients with missing data excluded from the analysis. Any spurious data values will be checked against

source material to verify the validity.

Clinical Investigation Plan

CONFIDENTIAL

Page 29 of 42

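### The 5-year re-rupture percentage is taken only from patients reached by telephone, and the stated Missing At Random assumption does not justify that crude estimate

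*SAP*

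**What the plan says.** **Source of the outcome.** Protocol 9.2 and 9.4.5 allow the call at 5 years or later only with verbal consent. In a sentence that opens "Retrospective data will", Protocol 9.2 adds that the record data are kept even when consent is not given. Under Protocol 9.7, a patient without a call finishes the study at the 6 to 24 month record window. Protocol 9.3 defines enrolment by the eligibility criteria alone, so such a patient is enrolled.

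**Missing data.** SAP 7.4 states: "Missing data will be assumed to be Missing At Random. No imputation procedures will be employed to deal with missing data". Protocol section 12 agrees: it rules out imputation and has "patients with missing data excluded from the analysis". SAP 7.2 limits the exclusion to the outcome concerned: "Patients with missing data at a specific outcome timepoint will be excluded from this dataset only for the particular outcome for which they had missing" (last word cut).

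**Analysis.** SAP 9.1 reports the number and percentage with a re-rupture at each timepoint, with a 95% confidence interval. SAP 8.1 bases percentages on the non-missing sample. SAP 6 allows for 20% drop-out, from 120 to 96.

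**Data held on patients not called.** Age, sport, autograft use, fixation and failure status up to 24 months come from the records (Protocol Table 1, SAP 5.3). The early follow-up, and sport before the call, are collected only where available.

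**Who is called.** SAP 5.1 says that "all participants will receive a telephone call to collect patient reported outcomes". Protocol section 8 likewise describes a call for each enrolled subject. Neither fits the consent rule in Protocol 9.2.

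**The concern.** Missing At Random lets the chance of being reached depend on observed variables such as age, sport or an early failure. An estimate that is valid under that assumption has to use those variables, for example by weighting, imputation or a time-to-event analysis. The planned percentage uses none of them. It needs the stronger condition that being reached is unrelated to re-rupture.

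That condition could fail in either direction: patients with a poor result may be less willing to take the call, or more willing. The documents give no evidence on this. The reported confidence interval reflects sampling error only, and neither document plans a comparison of reached with unreached patients or a sensitivity analysis.

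There is also a gap in the outcome rule. SAP 4.2.1 defines the primary endpoint as whether a re-rupture has occurred. A re-rupture recorded at, say, 12 months settles that for good, yet nothing says that it counts in the 5-year figure if the patient is never called.

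**Working it through.** **1. The plan's own figure.** Inputs from SAP 6: p = 0.10, half-width d = 0.06, 95% confidence, 20% drop-out.

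n = 1.96² × 0.10 × 0.90 / 0.06² = 96.04, so 96; then 96 / 0.80 = 120.

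Both figures reproduce. The inflation to 120 protects the width of the interval (half-width 6.0 points at n = 96). It does nothing about bias from who is missing.

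**2. What the plan would report.** Assume that the whole 20% allowance is failure to reach, so 24 of 120, and that 10 of the 96 reached have re-ruptured. The estimate is 10/96 = 10.4%. The SAP names no interval method. Wilson gives 5.8 to 18.1 and Clopper-Pearson 5.1 to 18.3.

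**3. Effect of the missing group.** Let m be the share not reached, and let p_R and p_U be the cumulative rates in reached and unreached patients.

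Rate over all enrolled = (1 − m) p_R + m p_U, so the shift from the reported figure is m (p_U − p_R).

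| Assumption for the 24 not reached | Re-ruptures over 120 | Rate | Shift from 10.4% |
|---|---|---|---|
| None (lower bound) | 10 | 8.3% | −2.1 points |
| Same rate (2.5 expected) | 12.5 | 10.4% | 0 |
| Twice the rate (5/24) | 15 | 12.5% | +2.1 points |
| One in three (8/24) | 18 | 15.0% | +4.6 points |
| All (upper bound) | 34 | 28.3% | +17.9 points |

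A shift equal to the 6-point margin needs p_U − p_R = 0.06 / 0.20 = 30 points, so a rate of about 40% in the unreached. If more were missing, less would be needed: with p_R = 10%, a rate of 30% at m = 0.30 and 25% at m = 0.40. Those larger shares are assumptions.

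**4. Chart-recorded re-ruptures.** If 4 of the 24 unreached have a re-rupture in the chart and are excluded for want of a call, the reported figure stays at 10.4%. At least (10 + 4)/120 = 11.7% are already known to have failed. With 8 it is at least 18/120 = 15.0%. These are minimum values, because later failures in the unreached are unknown.

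**5. What a comparison of the two groups could show.** With an assumed early failure rate of 5% in 96 reached patients, a test against 24 unreached has power of about 19% if their rate is 10%, 63% if 20% and 89% if 30% (normal approximation, rough at these counts). The comparison should therefore be descriptive.

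**The case against.** The strongest reply is that this is a descriptive single-group follow-up with no hypothesis test on the primary endpoint, and that the plan does provide for loss: SAP 6 allows for it, and SAP 7.2 and 7.4 say how missing values are handled. The moderate scenarios stay inside the sampling interval. A reader who knows the number enrolled and the number analysed could work out the extreme bounds. All of this stands, and it limits the weight of the point. It does not repair the mismatch between the stated assumption and the estimator.

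Four stronger readings are tempting, and the documents do not support them.

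- *The collected data could test Missing At Random.* They cannot. They can show whether being reached depends on observed variables. Dependence on the unseen outcome stays untestable.
- *Patients not called are dropped from the study.* SAP 7.2 excludes them only for the missing outcome, and SAP 9.1 reports each timepoint, so their early records can enter the earlier tallies. They would leave the Full Analysis Population, and the safety population with it, only if the 5-year follow-up condition in SAP 7.2 meant a completed call. SAP 5.1 suggests time since surgery, but SAP 7.2 does not settle it.
- *The SAP ignores the loss.* The sentence in SAP 5.1 about calling everyone is loose and conflicts with Protocol 9.2, but SAP 6, 7.2 and 7.4 show that loss is expected.
- *Non-response matters as much as the 6-point margin.* The moderate scenarios move the estimate by 2.1 and 4.6 points. Only rates of about 40% or more in the unreached reach 6 points at the planned loss.

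**Conclusion.** The point holds in this form: SAP 7.4 names an assumption that does not support the crude 5-year percentage, nothing in the plan shows how far non-response could move it, and the treatment of chart-recorded re-ruptures in patients not called is unstated. At the planned 20% loss and an assumed 10 re-ruptures in 96, plausible departures shift the figure by about 2 to 5 points, within logical bounds of 8.3% to 28.3%. The documents give no rate for unreached patients and no non-response figure beyond the 20% allowance, so these sizes are illustrations and the direction of any bias is unknown. The sample size of 96 evaluable and 120 enrolled is unaffected.

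**What to change.** 1. In SAP 7.4, replace the Missing At Random sentence with: *The crude percentage assumes that being reached is unrelated to re-rupture.*
2. Add a supporting analysis over all enrolled patients in which a chart-recorded re-rupture counts as a re-rupture in the 5-year figure, whether or not the patient was called.
3. Pre-specify a descriptive table of reached against not-reached patients by age, sport, autograft use, site and record-based re-rupture to 24 months. Note that the records may be incomplete, and that the table can show dependence on observed variables but cannot test Missing At Random.
4. Pre-specify a sensitivity range for the cumulative 5-year percentage over all enrolled patients. Set the total cumulative rate in the not-reached group at 0, 1, 2 and 3 times the rate in the reached group, never below the chart-recorded count, and add best-case and worst-case bounds. Using the total cumulative rate avoids counting early failures twice.
5. Reconcile SAP 5.1 and Protocol section 8 with Protocol 9.2, so that both refer to consenting participants.

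The cost is one table and a few sensitivity lines from data already being collected. The downside for the sponsor is a wider reported uncertainty.

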# 8 Summary of Study Data

## 8.1 Descriptive Analysis Methods

Continuous variables will be summarised using the number of (non-missing) datapoints, mean and standard deviation if found to follow a normal distribution. Continuous variables not found to be normally distributed will be summarised by the number of datapoints, median and inter-quartile range. Categorical variables will be summarised by the frequency and percentage (based on the non-missing sample size) of values in each category.

## 8.2 Demographic and Baseline Variables

A summary of patient demographics and baseline measurements are outlined in Section 5.3.2. Descriptive statistics will be produced for these variables, along with baseline values of the secondary outcomes. Summaries will be produced for each site separately, and for all patients combined. The summary statistics will be produced in accordance with section 8.1.

# 9 Efficacy Analyses

## 9.1 Primary Efficacy Analysis

The primary endpoint is re-rupture, assessed as a binary outcome (yes/no). The number and percentage of patients experiencing a re-rupture at each timepoint will be reported. Additionally, a corresponding 95% confidence interval will be reported for the percentage of patients with a re-rupture.

The summary statistics for the outcome variable will be produced in accordance with Section 8.1. The primary study analysis will be performed using the Full Analysis Population (see section 7.2).

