## 9.4.3 Medical record follow up, from surgery to 6 months (Data collection from medical notes, if available)

Follow up data from surgery to 6 months will be collected retrospectively to be used to fulfil the follow up requirements:

- Date of follow up.
- Reconstruction Failure (any graft failure and if so, what, when and how?).
- Details of any complications or revision of the reconstruction (including date, and cause of failure if known).
- Patient reported outcome score e.g. IKDC Subjective Knee Evaluation,
   Lysholm knee scoring scale, Tegner Activity.

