# 9.4.4 Medical record follow up, 6 months to 24 months (Data collection only, if available)

Follow up data from 6 months to 24 months will be collected retrospectively to be used to fulfil the follow up requirements:

- Date of follow up.
- Reconstruction Failure (any graft failure and if so, what, when and how?).

• Details of any complications or revision of the reconstruction (including date, indication and cause of failure if known).

• Patient reported outcome score e.g. IKDC Subjective Knee Evaluation, Lysholm knee scoring scale, Tegner Activity.

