9.4.5 Telephone call follow up (at least 5 years post-surgery)

A patient telephone follow-up will be conducted only on subjects who have given

verbal informed consent. Please refer to Informed Consent procedure Section 9.2

The following will be collected during the telephone follow up

• Verbal consent (ensure this process is documented).

• Date of Follow Up.

• Participation in sports.

• Reconstruction Failure (any graft failure and if so, what, when and how?).

• Details of any complications or revision of the reconstruction.

• Completion of IKDC Subjective Knee Evaluation.

• Completion of Lysholm and Tegner scores.

The IKDC, Lysholm and Tegner scoring at final follow up, must be completed by hand and filed within the site file. Paper copies will be provided to each site participating in the study.

Lysholm and Tegner final follow up scores will be entered directly into the Electronic Case

Report Form. IKDC at final follow up will be collected and calculated by the sponsor and

scores will be included in the final clinical report.

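### Re-rupture percentages for surgery to 6 months and 6 to 24 months rest on whichever patients have a record in that window, so they are open to bias and cannot be read as a course over time

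*SAP*

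**What the plan says.** SAP 9.1 treats re-rupture as a yes/no outcome and plans this output: "The number and percentage of patients experiencing a re-rupture at each timepoint will be reported". It adds: "The summary statistics for the outcome variable will be produced in accordance with Section 8.1". SAP 8.1 then fixes the denominator: "Categorical variables will be summarised by the frequency and percentage (based on the non-missing sample size) of values in each category". SAP 7.2 says: "Patients with missing data at a specific outcome timepoint will be excluded from this dataset only for the particular outcome" concerned. SAP 7.4 allows no imputation and states: "Missing data will be assumed to be Missing At Random".

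Table 1 in SAP 5.3.1 marks re-rupture in three columns: surgery to 6 months, 6 to 24 months, and 5 years. It puts no condition on the first two. The protocol does. The heading of Protocol 9.4.3 carries the words "Data collection from medical notes, if available", and that of 9.4.4 the words "Data collection only, if available". Protocol Table 1 has the same limit in its column headings.

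The final telephone call (Protocol 9.4.5) asks about "Reconstruction Failure (any graft failure and if so, what, when and how". It is made only to patients who give verbal consent (Protocol 9.2).

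**The concern.** The first two timepoints are not scheduled visits. They are whatever routine notes a site happens to hold. If a window without a note counts as missing, the denominator is the set of patients who came back, and coming back may well depend on whether the graft failed.

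The rule also sets aside information that the study will hold. A re-rupture is a dated event. A patient who reports at the call that the graft never failed is thereby known to have been free of failure in both earlier windows. A patient who reports a failure is asked when it happened. Using those answers is not imputation.

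At stake are the early percentages that SAP 9.1 places within the primary efficacy analysis. Three figures on three different denominators would invite a reader to see a trend that may only reflect how complete the notes are. SAP 9.2 acknowledges that knee scores before 5 years may not be obtainable. SAP 9.1 has no such caution for re-rupture.

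**Working it through.** **The plan's own figure.** Inputs from SAP 6: expected rate p = 0.10, half-width d = 0.06, 95% confidence. n = 1.96² × 0.10 × 0.90 / 0.06² = 96.04, stated as 96. Allowing for 20% drop-out, 96 / 0.80 = 120. The sample size reproduces. It rests on the overall rate, so this point does not touch it.

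**Formula for a window percentage.** Let N be the patients, e the failures in the window, f the share of failures with a note and a the share of non-failures with a note. Under SAP 8.1 and 7.2, with an empty window counted as missing:

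reported % = e·f / (e·f + (N − e)·a)

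The documents give no values for e, f or a. All values below are assumptions.

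**Illustration 1.** N = 120, e = 4 in the 6 to 24 month window, f = 1. True value: 4/120 = 3.3%.

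| a | Calculation | Reported |
|---|---|---|
| 80% | 4 / (4 + 0.8 × 116) = 4/96.8 | 4.1% |
| 50% | 4 / (4 + 0.5 × 116) = 4/62 | 6.5% |
| 30% | 4 / (4 + 0.3 × 116) = 4/38.8 | 10.3% |

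**Illustration 2, direction.** N = 96, with 2 failures by 6 months and 4 from 6 to 24 months. True values: 2/96 = 2.1% and 4/96 = 4.2%.

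| Assumption | 0 to 6 months | 6 to 24 months |
|---|---|---|
| f = 1, a = 80% | 2.6% | 5.2% |
| f = 1, a = 60% | 3.4% | 6.8% |
| f = 1, a = 40% | 5.1% | 9.8% |
| f = a (notes unrelated to failure) | 2.1% | 4.2% |
| f = a/2 (failures half as likely to be noted) | 1.1% | 2.1% |

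The sign of the bias depends on whether f is larger or smaller than a.

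**Illustration 3, course over time.** N = 96, 3 failures in each window, so 3.1% in both. With f = 1, suppose 80% of non-failures have a note in the first window and 40% in the second. The reported figures are 3 / (3 + 0.8 × 93) = 3.9% and 3 / (3 + 0.4 × 93) = 7.5%. The rate appears to double although nothing changed.

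**Check on the repair.** It matters how non-callers are handled. Assume 120 patients, 10 failures, all noted, and 80% reached regardless of outcome. The true rate is 10/120 = 8.3%. Callers alone give 8/96 = 8.3%. Keeping all 10 noted failures but only the 0.8 × 110 = 88 reached non-failures gives 10 / (10 + 88) = 10.2%. That would carry the selective denominator into the headline rate.

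**The case against.** The strongest reply is that the SAP is unclear here more than wrong. It does not say that a window without a note is missing. It does not forbid using the call to settle earlier windows, and it leaves open whether the percentages are cumulative or per interval. This stands in part. But the non-missing denominator and the exclusion of patients without data at a timepoint are stated rules, and nothing in either document says that an empty window counts as no failure or is filled from a later source. An analyst who followed the text would most naturally arrive at the selective denominator.

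The second reply concerns weight, and it stands. The protocol's primary endpoint is failure at final follow-up (Protocol 7.3), Protocol section 12 plans one overall percentage with a confidence interval, and the sample size rests on that rate.

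A reader might also infer three stronger things that the documents do not support:

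- **That the early rates are inflated.** Upward bias needs failures to be noted more often than non-failures. That is plausible, because a failure tends to bring a patient back, but no figure on completeness of notes is given. Failures treated at another hospital would push the other way.
- **That the call already dates every failure.** It covers only patients who consent and are reached, and it relies on recall at least five years after surgery. For the others, participation ends with the 6 to 24 month records (Protocol 9.7).
- **That the primary result is compromised.** For a patient who completes the call, final status does not depend on notes in the earlier windows.

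**Conclusion.** The point holds for the two early windows. Read as written, SAP 9.1 with 8.1 and 7.2 gives re-rupture percentages on self-selected and differing denominators, supported only by a missing-at-random assumption for which the documents offer no evidence. The figures are open to bias in either direction, more probably upward, and cannot be compared with one another or with the final rate.

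In the assumed cases where every failure is noted, the reported figure is about 1.2 to 3.1 times the true one (4.1/3.3 to 10.3/3.3). If notes are unrelated to failure, there is no bias. If failures are half as likely to be noted, the figure is about half the truth. These sizes rest on assumed numbers of failures and assumed completeness of notes. The final rate for patients who complete the call stands. The change is worth making before the analysis because it is cheap and the table would otherwise appear under the primary efficacy analysis.

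**What to change.** In SAP 9.1, replace the percentage per window with cumulative re-rupture by 6 months, by 24 months and at final follow-up. Place each failure by its date, from the records or the call, and state to which period the 6-month point belongs, since the two windows share it.

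Use one denominator at all three times: patients in the Full Analysis Population whose status at five years or more is known, whether or not they failed. Do not add noted failures from patients who were not reached while dropping unreached patients without a noted failure.

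To include non-callers, report instead a Kaplan-Meier cumulative incidence with its 95% confidence interval, censoring non-callers without a recorded failure at their last record. The SAP should then say that non-callers belong to the population used, because SAP 7.2 requires five years of follow-up.

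Under either option, report the number of patients with a note in each window.

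The cost is a paragraph in SAP 9.1 and a short derivation from dates already collected; no new data are needed. There are three drawbacks. Recalled failure dates may be approximate. The common denominator represents all patients only if being reached is unrelated to failure. Censoring at the last record likewise assumes that loss of contact is unrelated to failure.
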